#### 9.5 Exclusion Criteria:

Subjects will be excluded if in the opinion of the Investigator, the individual meets any of the following exclusions:

- 1. Active local or systemic infection.
- 2. Loss of musculature, neuromuscular compromise or vascular deficiency in the affected limb rendering the procedure unjustified.
- 3. Poor bone quality, such as osteoporosis, where in the surgeon's opinion, there could be considerable migration of the prosthesis or a significant chance of fracture of the femoral shaft and/or the lack of adequate bone to support the implant(s).
- 4. Charcot's or Paget's disease.
- 5. For hemi-hip arthroplasty, any pathological condition of the acetabulum, such as distorted acetabuli with irregularities, protrusion acetabuli (arthrokatadysis), or migrating acetabuli, that would preclude the use of the natural acetabulum as an appropriate articular surface for the hemi-hip prosthesis.
- 6. The Subject is a woman who is pregnant or lactating.
- 7. Existing contralateral hip that was implanted *less than* 6 months from the date of surgery at the time of consent into this study.
- 8. Subjects requiring a **simultaneous** bilateral hip at the time of consent will be excluded; there can be only one Actis® study hip. This also means that even if another hip system is used for the contralateral hip during simultaneous THAs, the Subject will be excluded. As noted above, Subjects who have an existing contralateral total hip replacement *greater than*

CONFIDENTIAL Page 17 of 53
Version Date: May 7, 2018

DePuy Synthes / Actis® Total Hip System
Protocol #14014 / Version B

6 months postoperatively at the time of consent may be entered into this study if they qualify based upon the eligibility criteria and the approved labeling requirements.

- 9. Subject had a contralateral amputation.
- 10. Subject has participated in a clinical investigation with an investigational product (drug or device) in the last three months.
- 11. Subject is currently involved in any personal injury litigation, medical-legal or worker's compensation claims regardless of body system.
- 12. Subject, in the opinion of the Investigator, is a drug or alcohol abuser or has a psychological disorder that could affect their ability to complete patient reported questionnaires or be compliant with follow-up requirements.
- 13. Subject was diagnosed and is taking prescription medications to treat a muscular disorder that limits mobility due to severe stiffness and pain such as fibromyalgia or polymyalgia.
- 14. Subject has a medical condition with less than 2 years of life expectancy.

**Note:** Diabetes, at present, has not been established as a contraindication. However, because of the increased risk for complications such as infection, slow wound healing, etc., the physician should carefully consider the advisability of hip replacement in the severely diabetic patient.

**Caution:** Implants and trial components from different manufacturers or implant systems should never be used together.

### 9.6 Enrollment & Subject Identification (ID) Number

A study Subject is enrolled when they have been properly consented. Once consent is obtained, the Subject must be added to the study electronic data capture (EDC) system, which will automatically generate a unique Subject number. The first two digits of the Subject number represent the site identification number, followed by a hyphen, and three digits representing the sequential identification (e.g., Subject 10-001 is the first subject enrolled at site 10). The Subject's unique identifier assigned in EDC will be recorded on each page of the eCRF and all other clinical investigation documentation relating to that Subject.

Study-specific Subject questionnaires should not be completed until the study Subject has signed and dated the Informed Consent Document and has met all other eligibility criteria. Additionally, a Subject must meet the eligibility criteria in order to participate in the optional Patient Activity Tracking (ActiTrakTM) part of the study.

The Principal Investigator must document the Subject's participation in this study in the Subject's clinic and hospital notes.

CONFIDENTIAL Page 18 of 53
Version Date: May 7, 2018

DePuy Synthes / Actis® Total Hip System
Protocol #14014 / Version B

#### 10.1 Primary Objective

Two-year (2 year) information regarding the performance of the commercially available Actis® Total Hip System in order to obtain and evaluate the clinical outcomes on a series of cementless primary total hip arthroplasty (THA) and hemi-hip arthroplasty using clinical, radiographic and device and procedure related adverse event assessments.

#### 10.2 Primary Endpoint

Investigate the minimum 2-year postoperative functional performance for the Actis® Total Hip System as measured with the Harris Hip Score at minimum 2 years postoperatively for cementless primary total hip arthroplasty. All analyses including the primary endpoint analysis will be conducted on primary THA subjects and a summary for hemi-hip arthroplasty Subjects will be provided separately.

#### 10.3 Secondary Endpoints

- Harris Hip score at 3-months and 1-year
- Radiographic evaluation at 2-years postoperatively, inclusive of leg length discrepancy
- Type and frequency of AEs through 2-years postoperatively
- Device survivorship at 2-years postoperatively

#### 10.4 Tertiary Endpoints

- Change in Subject Outcomes (*i.e.*, FJS-12, HOOS and Hip Evaluation) will be measured and compared from preoperative to 6-weeks, 3-months, minimum 1-year and minimum 2-years.
- Patient tracking activities reported from the mobile ActiTrakTM application will be analyzed for pain, location of pain, mood/emotion, and activities of daily living and range of motion. Subject Satisfaction will be asked periodically after surgery. The range of time for these tertiary endpoints will be from the time of consent preoperatively through 3-months postoperatively.

#### 10.5 Study Design

A prospective, uncontrolled, non-randomized, multi-center study with a total of 255 Subjects to include a minimum of 225 Primary THA Subjects and a cohort with a minimum of 30 hemi-hip arthroplasty Subjects. All Subjects will be seen for a preoperative clinic visit at the time of consent, during surgery, and then at 6-weeks, 3-months, minimum 1-year, and minimum 2-years postoperatively.

Each site is expected to implant the number of Subjects as outlined in their clinical trial agreement; however, cohort reallocation (no greater than 40 Subjects per site) is permitted in order to meet timelines. Details regarding sample size are presented in **Section 16.9.** 

CONFIDENTIAL Page 19 of 53
Version Date: May 7, 2018

DePuy Synthes / Actis® Total Hip System
Protocol #14014 / Version B

#### 10.6 Optional (Electronic) Patient Activity Tracking Device

This clinical investigation will provide the opportunity for Subjects who are properly consented and deemed eligible for the study to join in a parallel and optional portion of the study – to electronically capture real-time patient activities of daily living (such as pain, location of pain, mood/emotion, activities of daily living and range of motion, Subject satisfaction will periodically be asked after surgery) from the time of consent preoperatively to 3-months postoperatively. If a Subject is unable or unwilling to provide the preoperative data, this will not preclude or delay them from enrollment. Subjects may also enroll in the Patient Activity Tracking on the day of their surgery and collect activities through the 3-month postoperative visit interval. This optional part of the study will be open for enrollment until 225 THA Subjects are treated; then, this part of the study will be closed. The fulfillment of 225 THA Subjects occurred June 5, 2017 and this portion of the study has now concluded with Version B of the protocol.

Patient Activity Tracking is a combination of a wearable watch-like device and a mobile application, specifically, the ActiTrakTM application. The wearable watch-like Patient Activity Tracking device will be linked (*i.e.*, electronically synced) to a downloaded mobile application (app) on the Subject's own well-functioning (and updated to the most current operating system version) smartphone. If the Subject does not have a smartphone the Sponsor can provide an Android tablet to help Subjects continuously track their postoperative outcomes in their natural environment, in real-time, and in a non-invasive manner. This type of patient direct data collection can improve data quality and method of collection and is potentially more sensitive to the changes in activities preoperatively compared to postoperatively (*e.g.*, not burdensome or possibly inconclusive like a paper diary).

Study sites and study Subjects are not required to join in the optional portion of the study.

For those eligible study Subjects who chose to participate, the wearable Patient Activity Tracking device will be provided to them by the study site (which has been provided by the Sponsor) and will be returned at the 3-month visit. The mobile ActiTrakTM app will linked to their smartphone (or the Sponsor provided Android tablet as noted above) via a downloaded mobile app. The linking of the Patient Activity Tracking device to the ActiTrakTM app on a smartphone or Android tablet is required in order for the collected data to securely import into the study's EDC system.

The combination Patient Activity Tracking device and the ActiTrakTM app will be used to passively (automatically) as well as objectively (manual or active Subject entries into a downloaded mobile application on either a smartphone or Android tablet) in order to collect activities of daily living. Some questions will occur weekly and others only monthly. **Appendix G** provides guidance and support for study sites and Subjects.

#### 10.7 Study Database

The study database has been validated in accordance with 21 CFR Part 11, European Commission's Directive on Data Protection and US Safe Harbor Certification. Prior to being released for importation of patient activity and study data, validation of the study level components will be conducted in

CONFIDENTIAL Page 20 of 53
Version Date: May 7, 2018

DePuy Synthes / Actis® Total Hip System
Protocol #14014 / Version B

accordance with approved user acceptance testing procedures. Access to this system will be controlled so that only authorized users will have the ability to enter into the system. The system is considered a closed system according to 21 CFR Part 11 Electronic Records; Electronic Signatures.

#### 10.8 Treatment Assignment

The Actis® Total Hip System is the only construct of interest in the study; there will be no control group. This is applicable to the treatment of both total and hemi-hip arthroplasty.

#### 11 RADIOGRAPHS

This study will accept radiographs for the preoperative interval taken prior to the study Subject's participation in this study up to -180 days before surgery as long as the radiographs meet the three protocol required views: Antero-Posterior (AP) Pelvis, AP Femur and Lauenstein Lateral. The -180 days preoperative is allowed to minimize a study Subject's unnecessary exposure to radiation. Further radiographic details are provided in **Appendix D**.

Leg length discrepancy (LLD) will be recorded by the independent radiographic reviewer (IRR) via the radiographs on the Hip Evaluation eCRF (and, optionally by the Principal Investigator, See **Section 16.12** Secondary Endpoints).

#### 12 SUBJECT EVALUATIONS

#### 12.1 Summary of Subject Evaluations

Diagnostic, demographic and operative information, clinical follow-up and applicable unscheduled (*i.e.*, unplanned or unscheduled that occur between the protocol defined visit windows) visits for each enrolled Subject will be documented on electronic case report forms (eCRFs) which have been developed specifically for this study. Subject completed Patient Reported Outcomes or PROs will be completed on source by the study Subject and then entered by the study site into the EDC system. The eCRF details that are to be used to collect and evaluate study Subject outcomes preoperatively, intra-operatively and postoperatively are listed below in **Table 4.** Patient reported outcomes (shaded in light blue) will be provided in hard copy (*i.e.*, paper) printed sets for completion by the study Subject during the clinic visit. Study sites should not enter any data into the EDC system until each potential patient has signed consent and is considered enrolled (**Section 15** defines the consent process and **Section 9.1** defines the Subject population).

CONFIDENTIAL Page 21 of 53
Version Date: May 7, 2018

DePuy Synthes / Actis® Total Hip System
Protocol #14014 / Version B

# 12.2 Table 4 Summary of Subject Evaluation and eCRFs

Tal	ole 4 Summary of Subject Evaluations and eCRFs
Subject History	Demographic and study entry criteria are documented on Subject History.
eCRF DM	The preferred timing of the Informed Consent process and preoperative
	data collection (with the exception of the preoperative radiographs – see
	Section 11) is from -90 to -1 days of the surgical event.
Harris Hip	The Harris Hip Evaluation will be used to clinically assess each Subject at
Evaluation	the preoperative and postoperative intervals specified in Section 6 Subject
eCRF HH	Management Study Schedule.
	Contained in Section H, Leg length, of the eCRF HH there is an OPTION to provide a measurement of each leg (surgical and non-surgical) pre- and postoperatively. This option applies to both cohorts: THA and hemi-hips. If manual leg length measurements are taken, there are checkboxes in Section H to record the measurement method: "Apparent", "True" and "Other".
	The "Apparent" manual method is measured using a tape measure from the umbilicus to the medial malleolus.
	The "True" manual method is measured using a tape measure from the anterior superior iliac spine to the medial malleolus (Sabharwal).
	"Other" consistent and repeatable LLD measurements are acceptable as per each study sites' standard of care.
	If leg length is manually measured and reported pre-operatively for a Subject, please be consistent and collect it for the entire study for analysis. Leg length discrepancy (LLD) will be analyzed ( Section 16.12 ) as a secondary endpoint.
Hip Evaluation	Subjects will complete a hip outcomes self-assessment, which includes
eCRF HE	questions about their satisfaction and hip function starting at the preoperative interval.
HOOS	Subjects will complete this hip outcomes self-assessment, which includes
eCRF HOOS	40 questions about their activities of daily living and more advanced sports and recreational activities starting at the preoperative interval.

CONFIDENTIAL Page 22 of 53 DePuy Synthes / Actis® Total Hip System Version Date: May 7, 2018 Protocol #14014 / Version B

Forgotten Joint Scale	Subjects will complete this hip outcomes self-assessment, which includes
(FJS-12)	12 questions about their awareness of their (operative) hip joint and their
eCRF FJS	ability to 'forget' the artificial joint in everyday life.
Pre- and	Radiographic guidelines are provided in Appendix D.
Postoperative Hip	
Radiographic	High quality Antero-Posterior (AP) Femur, AP Pelvis and Lauenstein
No eCRF for Study	Lateral radiographs of the operative hip will be obtained during the same
Site	preoperative and postoperative follow-up intervals as for the clinical
	evaluations. All original radiographs will be retained by the site and digital
	copies will be sent to the Sponsor through a web-based application.
	Alternate methods to submit radiographs to Sponsor must be pre-arranged.
	Analysis of the radiographs by an Independent Radiographic Reviewer
	(IRR) will involve the use of a web-based application.
	Observations by the IRR will be documented on the radiographic eCRF
	(radiographic eCRF is not provided to study sites) and entered into the
	study radiographic database by the IRR.
Operative Details	For all Subjects, detailed information related to the primary diagnosis,
eCRF OP	anesthesia type and time, if a fracture table (e.g., HANA Table) was
	utilized, and surgical exposure (e.g., anterior approach), and other surgical
	data will be recorded on the Operative Details eCRF – this includes
	primary total hip arthroplasty and hemi-hip arthroplasty.
Device Log	Labels for each component/device used during the procedure must be
eCRF DX	recorded.
Unscheduled Visit	An unscheduled office visit is defined as any visit at the study site where
Report	a study subject is seen by one of the site staff including the principal
(unplanned or	Investigator (PI), any Sub-investigator (as appropriate), and anyone
interim)	identified on the PI's team, outside of the scheduled study visit. An
	unscheduled visit is only to be reported when the visit falls between study
eCRF UNS	intervals as described in Section 6 Subject Management Study
	Schedule. An unscheduled visit eCRF is not to be completed if the
	Subject comes in for additional, unplanned visits within the in-
	window study interval.
	If the previous protocol defined study interval visit was missed, the
	required eCRFs/CRFs in the previously missed interval visit are also
	required along with the unscheduled visit eCRF.

CONFIDENTIAL Page 23 of 53
Version Date: May 7, 2018

DePuy Synthes / Actis® Total Hip System
Protocol #14014 / Version B

	If an unscheduled visit is related to a new, worsening, or resolved adverse			
	event, both an AE eCRF and the unscheduled visit eCRF are completed.			
Adverse Event (AE)	In the event of a postoperative AE the details will be captured on an AE			
eCRF AE	eCRF. Only one AE can be recorded on an AE eCRF.			
	An AE can be defined as Mild, Moderate or Severe and these terms are			
	defined in Section 13 (The definitions of Serious Adverse Event and			
	Unexpected Adverse Device Event or UADE are defined in Section 13 ).			
	Early responsible AE places resolve the previous AE on aCDE and remort			
	For a worsening AE, please resolve the previous AE on eCRF and report			
Dations Assisting	a "New" AE eCRF for the new Severity.			
Patient Activity	The Patient Activity Tracking device is a wearable watch-like device that			
Tracking (ActiTrak TM )	will be linked with the ActiTrack TM app that is downloaded on to a Subject's own smartphone (iPhone or Android phone, or Sponsor provided			
(ACHITAK )	Android tablet) and will be used at some sites. It is not mandatory for a			
eCRF PA	study site or a study Subject to participate. For details on the Patient			
CRITA	Activity Tracking device (i.e., the wearable watch-like device) and the			
	required downloaded mobile app, refer to Appendix G .			
	required do winouaca moone upp, terer to rependix G.			
	Preoperatively at from the time of consent through 3 months			
	postoperatively is the preferred timeline for participation.			
	Data collected via the Patient Activity Tracking is a part of the tertiary			
	endpoints (Section 16).			
End of Study/	Please complete the End of Study eCRF when a study Subject has either			
Withdrawal	completed the study primary endpoint (2-year follow-up) or for any reason			
	for withdrawal; some examples are listed below:			
eCRF DS	Withdrawal of consent			
	Investigator decision			
	• Death (correlate with AE eCRF)			
	Lost to follow-up			
	General screen failure (includes intra-operative screen failures)			
	Study site withdrew/terminated from study			
	Adverse event related (including revisions postoperative, correlate)			
	with AE eCRF)			
	• Other reasons – specify			
	Revision (correlate with AE eCRF)			
	Completion of final endpoint at minimum 2 years			

CONFIDENTIAL Page 24 of 53
Version Date: May 7, 2018

DePuy Synthes / Actis® Total Hip System
Protocol #14014 / Version B

NOTE: AE eCRF will be completed for only device and procedure related AEs. For further details and directions regarding revision of any study component please also refer to Table 8 Revisions and Reoperations.
All screen failures (SFs) are to be reported on the Screening and Enrollment Log (Log will be provided by the Sponsor).

## 12.3 Actions for Screen Failure Subjects

Subjects can be a screen failure prior to surgery (*e.g.*, withdraw of consent) or be considered a screen failure when withdrawn intra-operatively; intra-operative screen failure could be due to the Subject requiring a non-study implant. **Table 5** below provides further examples of screen failures and required actions.

# 12.4 Table 5 Actions for Screen Failure Subjects

	Table 5 Actions for Screen Failure Subjects (Based on the definition of an Enrolled Subject in Section 9)					
Screen Failure Type	Screening/ Enrollment Log?	Data submitted To EDC?	Enrolled Subject?	Example	Action	
Pre- operative screen failure	Yes	Yes	Yes	Subject signed IPC, meeting the definition of enrolled, but has withdrawn consent before surgery or no longer meets inclusion/exclusion criteria at time of surgery	Document on Screening & Enrollment Log as Preoperative Screen Failure  Complete & enter Preoperative eCRFs if data was collected: DM, HH, HE, HOOS and DS	

CONFIDENTIAL Page 25 of 53
Version Date: May 7, 2018

DePuy Synthes / Actis® Total Hip System
Protocol #14014 / Version B

Intra- operative screen failure	Yes	Yes	Yes	Subject signed IPC, meeting the definition of enrolled, but it was determined during surgery that the Subject would not have the Actis® Total Hip System implanted	Document on Screening & Enrollment Log as Intra- operative Screen Failure  Complete & enter Preoperative & Operative eCRFs if data was collected: DM, HH, HE, HOOS, PA and DS
--	-----	-----	-----	--	---

Overall, the number of study Subjects implanted with the Actis® Total Hip System, across all study sites, must meet the total sample size of 255 Subjects that includes a minimum of 225 Primary THA Subjects and a cohort of a minimum of 30 hemi-hip arthroplasty Subjects. Meaning, you can replace Subjects who have screen failed prior to implantation.

# 12.5 Actions for Postoperative Withdrawals

A postoperative withdrawal is a Subject who signed the IPC document, was implanted with the study device, and is later withdrawn from study participation (*i.e.*, withdrawal of consent, revision of femoral or acetabular components, death, etc.). **Table 6** provides examples and the actions and eCRF(s) to be completed at the time of withdrawal.

All data up to date of withdrawal will be included in the clinical analysis.

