#### 12.6 Table 6 Actions for Postoperative Withdrawal

Table 6 Actions for Postoperative Withdrawal					
Example	Actions	Follow -up			
Subject	Document Subject's request for withdrawal from				
withdraws	

the study in the source

Complete End of Study/Withdrawal eCRF

	Do not continue			
consent	Update Screen/Enrollment Log				
	Document in source				
D 41	Complete Adverse Event eCRF	Do not			
Death	Complete End of Study/Withdrawal eCRF	continue			
	Update Screen/Enrollment Log				
	See Section 14.5, Table 9 Revisions and	Do not continue if the			
Revision	Reoperations	femoral stem has been			
	Acopei ations	removed or revised.			

CONFIDENTIAL Page 26 of 53
Version Date: May 7, 2018

DePuy Synthes / Actis® Total Hip System
Protocol #14014 / Version B

	Please continue to follow
	if the femoral component
	has not been removed or
	revised

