## 14.5 Table 9 Revisions and Reoperations

A "**revision**" is defined as a surgical procedure of the affected study hip where any Actis® Total Hip System component for any reason is removed. A revision algorithm specifically for this study is as follows:

Table 9 Revisions and Reoperations			
Component(s)	eCRFs to be completed	Actions	
revised/removed			
All 4 components removed:	AE eCRF	Subject is revised and	
femoral stem and head,	End of Study eCRF	withdrawn from the study	
acetabular cup and liner			
Exchange of only the	AE eCRF	Subject is categorized as	
polyethylene acetabular liner		revised but not withdrawn from	
(only poly liners are allowed in		study	
the study)		Continue to follow through the	
		2-year endpoint	
Removal of only the femoral	AE eCRF	Subject is revised and	
stem and head (acetabular cup	End of Study eCRF	withdrawn from the study	
and liner remain in place)			
Removal of only the acetabular	AE eCRF	Subject is categorized as	
cup and liner (femoral stem		revised but not withdrawn from	
and head remain in place)		study	
		Continue to follow through the	
		2-year endpoint	

A "re-operation" is defined as any surgical procedure of the affected study hip in which **NO THA** components are removed. These subjects are not to be withdrawn. An **AE eCRF must be** completed (e.g., reoperation could occur to treat an infection).

All removed components are subject to further evaluation. If the implant is known to be available, the Sponsor will encourage the Investigator to preserve the prosthesis alone. In the event of a death, the excised hip joint with the implant in place should be provided to the Sponsor if possible. Please contact the Sponsor for details should a retrieved study implant become available.

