# 16.5 Handling of Missing Data

. Only actual subject data which is collected will be utilized in analyses.

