### 16.8 Analysis Sets

- This study will have 3 analysis sets which will be determined for both THA and hemi-hip Subjects as defined below and illustrated in the Data Flow Diagram: Enrolled Set is defined as all cases consented to participate in this study. The Enrolled Set will be used for the summary of disposition.
- Safety Set is defined as all cases that received the Actis® Total Hip System. The Safety Set will be used to summarize demographic characteristics, adverse events and survivorship;
- Per Protocol Set is defined as all Safety Set subjects without major protocol violations. The Per Protocol Set will be used for the summary of primary, secondary and tertiary endpoints.

CONFIDENTIAL Page 40 of 53
Version Date: May 7, 2018

DePuy Synthes / Actis® Total Hip System
Protocol #14014 / Version B

Figure 16-1: Analysis Set Flowchart

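### Section 12.5 treats acetabular revision as a withdrawal, Tables 6 and 9 keep stem-retained revisions in follow-up, and Table 4 points to the wrong table, so 2-year data could be lost

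*Combined protocol and SAP*

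**What the plan says.** - **Section 12.5** describes a postoperative withdrawal as an implanted subject who later leaves the study, and its bracketed instances include "revision of femoral or acetabular components, death, etc". It adds that "All data up to date of withdrawal will be included in the clinical analysis" and refers to Table 6 for the actions.
- **Table 6 (Section 12.6)**, Revision row, ends follow-up when the femoral stem has been removed or revised. When it has not, the instruction is "Please continue to follow". The row refers to Table 9.
- **Table 9 (Section 14.5)** sets out the revision algorithm. For a liner-only exchange, and for the row beginning "Removal of only the acetabular" (cup and liner out, stem and head kept), the subject is "revised but not withdrawn from" the study. Only an AE form is required, and follow-up runs to the 2-year endpoint.
- **Table 4 (Section 12.2)**, End of Study/Withdrawal, gives as example reasons "Revision (correlate with AE eCRF" and, separately, AE-related withdrawal with postoperative revisions included. A closing note sends sites for revision directions to a Table 8 titled Revisions and Reoperations. Table 8 (Section 14.1) defines relatedness; that title belongs to Table 9.
- **Section 16.5**: "Only actual subject data which is collected will be utilized in analyses". **Section 16.8**: "The Per Protocol Set will be used for the summary of primary, secondary and tertiary endpoints".
- **Section 16.12** censors cases without stem revision at last follow-up, death or withdrawal in the stem-survivorship analysis. **Section 13** ends AE reporting when participation ends.

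**The concern.** For one type of event, the revision of acetabular parts with the stem retained, the protocol gives two answers to whether the subject stays in the study. No section says which prevails. The reference that should settle it on the form ending participation carries the wrong table number. Section 18 does not require on-site interim monitoring, so a mistaken withdrawal might not be noticed.

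At stake is outcome-linked missing data. The trigger for leaving would be a revision, and Section 16.5 provides no imputation or other recovery of a value that was not collected. Sites could also differ in what they did, which would blur the by-site presentation planned in Section 16.10.

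**Working it through.** **1. The passages side by side, for a liner or cup-and-liner revision with the stem retained**

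| Place | Status of the subject | Form |
|---|---|---|
| Section 12.5 | Withdrawn, read literally | Defers to Table 6 |
| Table 4 | Revision is an example reason for ending participation, with no stem limit in the list; the note points to the right title under the wrong number | End of Study |
| Table 6 | Followed | Defers to Table 9 |
| Table 9 | Revised, followed through 2 years | AE form only |

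The conflict is confined to this case. Where the stem is removed, with or without the cup, every place ends follow-up. Section 19 describes the hemi-hip prosthesis as stem and head only, so the conflict concerns the THA cohort.

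**2. What a mistaken withdrawal would remove**

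- 2-year HHS and 2-year radiographs: lost, because only collected data are used.
- AEs after withdrawal: not collected.
- Stem survivorship: the subject is censored at withdrawal instead of contributing time to 2 years.
- Any-component survivorship: unaffected, because the revision is itself the event.

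**3. The plan's own precision figure**

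Inputs from Sections 16.9 and 16.11: about 200 THA subjects with a 2-year HHS, SD about 10, two-sided 95% interval.

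- Normal: 1.96 × 10 / √200 = 1.386
- t with 199 df: 1.394

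Both round to the stated 1.4 points. This point does not dispute that figure.

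**4. Illustrative shift in the mean HHS**

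If k of 200 subjects score d points below the rest and all k are dropped, the mean rises by (k/200) × d. The documents give neither k nor d; both are assumptions.

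| k (share) | d = 10 | d = 20 | d = 30 |
|---|---|---|---|
| 1 (0.5%) | 0.05 | 0.10 | 0.15 |
| 2 (1%) | 0.10 | 0.20 | 0.30 |
| 4 (2%) | 0.20 | 0.40 | 0.60 |
| 6 (3%) | 0.30 | 0.60 | 0.90 |

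A shift equal to the 1.4-point margin needs a dropped share of 1.4/d: 14% at d = 10, 7% at d = 20, 4.7% at d = 30. Precision hardly changes: the t-based half-width goes from 1.394 to 1.398 with one subject dropped and 1.416 with six.

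**The case against.** The strongest reply is that Section 12.5 does not set the follow-up rule. It offers a loose list and sends the reader to Table 6, which sends the reader to Table 9. Those two tables agree, are more specific, and keep these subjects. Table 4 gives only examples of reasons, must list revision in some form because stem revision is always a withdrawal, and has a note directing sites to a table by the title of the revision algorithm. A site would have to stop at one parenthesis, or be misled by a wrong number, before any data were lost.

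Much of this stands. A reader might infer that the End of Study form makes every revision a withdrawal without qualification. The note in Table 4 rules that out, although its number is wrong. A reader might also infer that subjects have already been withdrawn in error; nothing in the documents shows that.

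What survives is that 12.5 names acetabular revision as sufficient for withdrawal while Table 9 says it is not, and that the form's reference to the correct rule lands on an unrelated table. The consequence falls on the primary endpoint, so this is more than a typographical matter.

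**Conclusion.** The inconsistency is real and worth correcting, but its effect depends on sites not reaching Tables 6 and 9, and its size cannot be determined from the documents.

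A reader might infer an upward bias in the mean HHS of up to about two-thirds of the margin of error (0.9/1.4 = 0.64). The documents do not support that as an estimate. It needs 3% of subjects, a 30-point deficit and misapplication to every one of them, all together. Even the direction assumes that a revised hip still scores lower at the 2-year visit, on which the documents are silent. Every illustrated scenario stays below 1.4 points, and Sections 16.3 and 16.7 set no hypothesis against which a conclusion could change.

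Nor would the main survivorship result lose the event: removal of any component is counted whether or not the subject is then withdrawn. Only stem survivorship would lose follow-up time. The separate loss of subjects whose stem is revised occurs under every passage and would remain after this correction.

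**What to change.** 1. Reconcile Section 12.5, Table 4, Table 6 and Table 9 to one study follow-up rule. The rule already in Tables 6 and 9 is the one that preserves the endpoint data.
2. Align the parenthesis in 12.5 and both revision-related reasons in Table 4 with the rule chosen.
3. Correct the Table 4 note so that it refers to Table 9.
4. Tell sites by memo.
5. Have the sponsor check End of Study forms for any stem-retained revision recorded as a withdrawal. Consider re-contact only if one is found and consent allows.

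The cost is a few wording edits, a memo, a short data check, and the IRB/REB/EC submission that Section 22.6 requires even for administrative changes. Sample size and the stated margin of error do not change.
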